We will use REDCap software to collect and organize study data including information collected on the screening check list, recruitment and enrollment and retention data, group attendance, study participation, exit interview, and follow up interview data. We will also obtain consent signatures electronically using REDCap.

Please note that the wording described in all participant-facing documents and questionnaires may be modified slightly to improve word choice or correct typos or other errors.

We will use Zoom features such as sharing our screen, white board, polls, and waiting room to enhance learning and protect integrity of group sessions.

We will teach basic Zoom skills (how to raise your hand, how to use the chat box, etc.).

5.

5.2. **Procedures.** This study will be advertised to be a study of “journaling in recovery from addiction.” All those interested in the study will be screened first by NUWAY staff to see if they meet basic criteria (see “prescreening guide for NUWAY staff,” attached) and then by research staff (using Zoom for electronic administration, see screening procedures, below). After screening and administration of the baseline assessment battery, individuals will be randomized into treatment and control groups using randomly generated pairs of numbers or using REDCap’s randomization procedure.

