- 9.2. Exclusion Criteria: 1) presence of a psychotic disorder, psychiatric condition (e.g., suicidal ideation), or cognitive impairment (e.g., severe dementia, traumatic brain injury) limiting ability to give consent and/or participate in the study; 2) severe psychiatric illness (current schizophrenia, major depression with suicidal ideation); 3) personality disorders that would interfere with satisfactory participation in or completion of the study protocol, 4) inability to give informed, voluntary consent to participate, 5) lack of sufficient English literacy to participate, defined as inability to make a list of 5 things they did yesterday and inability to understand Qualtrics survey questions, 6) any impairment, activity, or situation that in the judgment of the research staff would prevent satisfactory participation in or completion of the study protocol, 7) the unlikely event that the participant is already doing something very similar on a daily basis such as a written 10th step and a daily action plan, 8) no access to a phone/tablet or internet connection.

7. See the attached document “Recruitment, Screening, Consent, and Baseline Script.” This document shows how each of the inclusion/exclusion criteria will be assessed during the recruitment and screening phase of the study.

- 9.3. Screening: The screening process will proceed as follows.
 - 1) NUWAY staff will identify clients who might be eligible. NUWAY staff will complete the “pre screening guide” to make sure that a client meets basic study criteria. Prospective participants who meet these criteria will be

PROTOCOL TITLE: Journaling and Addiction Recovery

VERSION DATE: 13 April 2021

given a study flyer (see attached, an electronic version of the flyer will be sent to clients), and will have the opportunity to sign up to have an appointment with Research Staff at NUWAY to continue the screening and informed consent process, or call research staff to ask questions.

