5. Participants may also be placed on the waiting list if: a) they will not be at NUWAY for the duration of the study, b) research staff is not sure if the person is eligible based on results of screening tests. In this case, NUWAY counseling staff are consulted to make sure the participant is eligible (e.g., if the person is adequately stabilized psychiatrically for participation).
6. Participant will be asked to write a list of 5 things that happened yesterday, research staff will evaluate this list and determine whether or not it is adequate for study inclusion. If not adequate, screening procedure will stop.
7. Research staff will administer the GAIN Cognitive Impairment Screener.⁵⁷ This instrument uses 6 items to determine cognitive impairment. It uses questions such as “What year is it now?” and “Please count backwards from 20 to 1.” Participants earn points for correct answers. Cognitive impairment is considered to be present if the total score is greater than 10. If the participant scores 14 or greater, they will be excluded from the study. Screening procedure will stop.

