“in the last week” would mean in the week that ends today. Please know I will not be asking you any follow up questions for any of these next questions. Depending on some of your answers, I might need to let NUWAY staff know of your replies.” We would consider a high score to be two or more past-week symptoms for each subscale: internalizing disorder, externalizing disorder, or criminal/violent behavior. Exclusion from the study based on these items would include endorsing “last week” for certain items such as: “thinking about ending your life or committing suicide,” “lied or conned to get things you wanted or to avoid having to do something,” having a hard time “paying attention at school/work/home” in combination with having a hard time “listening to instructions at school/work/home,” “were a bully or threatened other people,” “started physical fights with other people,” “had a disagreement in which you pushed, grabbed, or shoved someone,” and “purposely damaged or destroyed property that did not belong to you.” In the event of high scores in any of the three subscales or a single score of “last week” for any of these selected items, the person would not be eligible for the study. However, in each of these cases, we would discuss the results with NUWAY staff before determining final eligibility for the study.

8. The requirement of 2 weeks continuous sobriety before enrollment in the study may be waved based on clinical judgment.
9. Participant would read/review/discuss with study staff the informed consent/HIPAA consent combined document. Participant would read/review/discuss with study staff the HIPAA consent document.
10. Research staff would ask the participant the questions from the UBACC quiz to determine capacity to consent.⁵⁷ A score of 15 or higher is needed for inclusion in the study. The prospective participant can review the study details and return to re-do the quiz another day if this is possible given the study timeline.
11. If they score over 15 on the UBACC and meet all other study inclusion/exclusion criteria, or if they are eligible for the wait list, they will sign the main informed consent document (electronically if electronic administration). These forms will be signed in duplicate, providing one copy for research staff and one for participant (duplication unnecessary for electronic administration).
12. If the participant is deemed to meet all study criteria, they would move on to take the baseline assessment instrument.

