13. Participants will be asked to provide the names and contact numbers/email addresses for 2 people who will always know where they are. This information will be collected via the screening check sheet (information from the screening check sheet will now be administered via Redcap with data captured in Redcap rather than on paper) and will be used to help invite the participant to the exit interview/follow up interview. At the end of the exit interview, participants will be asked how best to reach them for the follow up interview 30 days later. Final Target gift cards will be disseminated electronically. (At the follow up interview, the control group will be mailed a copy of the journal and journal instructions and so we will make sure to obtain their mailing address).
14. Before randomization, participants will be asked, "In this study you will be assigned to either the Gold or Maroon groups. How do you feel about the fact that you would be helping us either by the Gold group activities or the Maroon group activities? How willing would you be to do your best whether you end up in the Gold or Maroon group? Are you willing to participate even though you might not get the group of your first choice? For our research it is important to get a good response rate. This means participating in study activities as much as possible. Do you agree to help the project in this way?" Responses will be recorded on the screening check sheet. (information from the screening check sheet will now be administered via Redcap with data captured in Redcap rather than on paper)
15. If admitted into the study, participants will be randomized into treatment and control groups. The treatment group is the "maroon" group the control group is the "gold" group (University of Minnesota school colors).
16. If participants decide not to participate when they hear their group assignment, we will ask them why and record their answers on the screening check sheet. (information from the screening check sheet will now be administered via Redcap with data captured in Redcap rather than on paper)
17. Each group will receive instructions for their arm of the study (See "instructions for Maroon and Gold Groups v2," attached).

10. Vulnerable Populations

10.1. Vulnerable Populations:

Children

- Pregnant women/Fetuses/Neonates
- Prisoners

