Interested clients will contact research study staff by phone, email, or text. Whenever possible, study staff will conduct a preliminary screening and if the participant appears eligible, make an appointment for the screening interview. When a preliminary screening is not possible, the preliminary screening questions will be the first questions asked at the screening interview. The preliminary screening questions are designed to determine as quickly as possible when a person might be eligible for the study and will be conducted via a brief telephone call. The preliminary screening questions are as follows: 1. Are you now a client at NUWAY? 2. How long have you been a client at NUWAY? (6 day minimum is required). 3. What is

your latest date of sobriety? (6 day minimum is required). 4. Are you at least 18 years old? 5. Who is your counselor and what NUWAY facility are you attending? 6. If you are part of this study, you might be asked to join a zoom group that meets from [insert time of group, e.g., 12 to 1 pm] on 8 weekdays, starting [insert start date]. Would that work for your schedule? 7. If you are part of this study, we'll be contacting you by email regularly. Would you be willing to check your email daily? 8. How is your ability to read and write in English? 9. Do you have a device (smartphone/tablet) that has a camera in it, and can connect to the internet? Would you be willing to use this device for the research study? 10. Are you able to attend Zoom meetings for the research study? 11. Are you able to fill out electronic questionnaires that we will send to you? 12. What questions can we answer about the research study?

At the screening interview, research staff will guide prospective participants through the screening informed consent, regular informed consent procedure, take the baseline questionnaire, and be randomized into the treatment (maroon) or control (gold) groups. Individuals who meet criteria for the waiting list would also have the opportunity to take the baseline screening instrument.

12.2. Source of Participants: All participants to be enrolled in the study will be concurrently receiving SUD treatment at NUWAY Inc. Study participation is offered in addition to SUD treatment as usual, but participants may miss NUWAY groups in order to instead attend PPJ groups. This decision will be made by NUWAY staff. During COVID19, our groups will be offered at times other than NUWAY core remote treatment groups whenever possible.

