As of August 2020, we will also be recruiting from a second NUWAY site, "NUWAY III." NUWAY III is located at [name]. NUWAY III is a medium-intensity residential treatment program for women and transgender people. The program provides comprehensive treatment for substance use and mental health disorders and has the capacity for 31 women and transgender people. NUWAY III offers gender-informed curriculum, treats trauma, and offers individual and group therapy.

As of September 2020, we will also be recruiting from a third NUWAY site, "2118." Nuway's [name] location in Minneapolis, MN, serves over 220 outpatients each year. Nuway is an extended care outpatient facility where clients attend treatment 4 hours per day, Monday through Friday, for 90-120 days. "2118" is a 20,000 square foot facility featuring 10 group rooms, 16 offices assigned to counseling staff, five therapy offices, several client lounges including five designated as quiet

areas, a cafeteria for clients, a lecture hall that seats 135 people, a smoking area, and an outdoor green space. “2118” has 15 full-time licensed clinicians, two clinical supervisors, one program director, one executive program director, three admissions staff, three information technology support staff, 6-10 interns from various counseling programs throughout the Twin Cities, and 2-4 floating therapists who fill in as needed.

All study procedures are the same for all NUWAY sites.

2. International Research: N/A
3. Community Based Participatory Research: N/A

2. Multi-Site Research

N/A

3. Resources Available

3.2. Resources Available:

Time. The Agricultural Experiment Station (AES) grant that is funding this study provides PI [name] with one course buy out for the academic year 2019-2020. PI [name] will use this time and additional time to conducting and completing this research.

Research Assistant(s) (RA). The AES grant that is funding this study allows for two 25% RAs for the 2019-2020 school year and two 25% RAs for the 2020-2022 school year. One RA will be dedicated to this study. The CTSI grant will also provide a second RA. The RAs will be involved in all aspects of the research including screening and informed consent, data management, data cleaning, literature reviews, exit interviews, attending group sessions, and general research activities.

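### Allocation may be by undefined pairs of numbers with no concealment stated, so staff with eligibility discretion could foresee up to half the assignments; the arm comparisons also ignore the residential/outpatient difference

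*Combined protocol and SAP*

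**What the plan says.** **Method.** Section 5.2 (Procedures) says that, after screening and baseline, people are allocated "using randomly generated pairs of numbers" or, as an alternative, by REDCap. This is the only description of the method. The protocol gives no allocation ratio, block size, list holder, concealment or stratification.

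**Timing.** Under Section 12.1 a prospective participant attends a screening interview to go through consent, "take the baseline questionnaire, and be randomized into the treatment (maroon) or control (gold) groups". Section 9.3, step 16, adds: "If participants decide not to participate when they hear their group assignment, we will ask them why". The arm is therefore disclosed at once, and no blinding of research staff is described.

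**Discretion over entry.** Section 5.1 makes study staff responsible for final screening and consent. Section 9.2 excludes for "any impairment, activity, or situation that in the judgment of the research staff would prevent satisfactory participation". Section 9.3, step 5, allows wait-listing when "research staff is not sure if the person is eligible based on results of screening tests". Step 8 says: "The requirement of 2 weeks continuous sobriety before enrollment in the study may be waved based on clinical judgment". Under Resources Available, research assistants take part in all aspects of the work, including screening, consent and group sessions.

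**Sites.** Section 23.1 lists 3R's (intensive outpatient), 2118 (outpatient) and a third site: "NUWAY III is a medium-intensity residential treatment program for women and transgender people". Neither the Analysis Plan in Section 5.2 nor Section 17.3 has a term for site or setting, and the Multi-Site Research section is marked not applicable.

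**The concern.** Randomisation protects a comparison only if whoever decides on entry cannot foresee the next assignment. Here the staff deciding on entry would see each arm as it is announced, and they have several legitimate ways to admit, defer or decline a borderline person. If the next arm can be worked out, those decisions can drift with it, without any intent.

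Retention and substance use are named as primary outcomes in Section 3.1, alongside feasibility and acceptability. Section 17.2 claims adequate power for retention with a two-tailed test, and Section 17.3 plans arm comparisons and will use the results to size a larger trial. A selection effect would carry into all of these.

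Setting is a smaller, separate matter. Residential and outpatient clients may well differ in retention and in how substance use is detected. A chance imbalance in setting would then add noise that the planned analysis does not remove.

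**Working it through.** The plan gives no figure for predictability or site balance, so there is none to reproduce on this point. Its power figures in Section 17.2 (.61, .34, 94%, .82 at N=76) do reproduce with the arcsine approximation at an assumed 38 per arm (0.609, 0.344, 0.942, 0.815), but they do not bear on allocation.

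**Inputs.** Target of about 100 (Section 11.1); waves of 10-20 (Section 8.1); the two methods in Section 5.2. Equal allocation is an assumption, because no ratio is stated.

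**1. Predictability, if earlier assignments are visible and people are entered one at a time.**

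- *Block of two.* The first assignment is a coin toss and the second is certain. Certain share = 1/2, so 50 of 100. Correct guesses = (0.5 + 1)/2 = 75%.
- *Fixed, known block of four.* The first two agree with probability 1/3, which fixes the last two; otherwise only the last is fixed. Certain share = (1/3 × 2 + 2/3 × 1)/4 = 33%. Correct guesses = (1/2 + 2/3 + 2/3 + 1)/4 = 71%.
- *Fixed, known block of six.* By enumeration, 25% certain and 68% guessable.
- *Random unannounced blocks of four or six.* Always guessing the arm that is behind is right about 69% of the time (simulation).
- *Concealed simple randomisation.* 0% certain, 50% guessable.

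Moving from 75% to 69% is a modest gain. Hiding the running sequence from those who decide eligibility does more than changing the block size.

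**2. From predictability to bias.** If discretion on the known slots shifts a prognostic factor by δ SD between arms, the overall shift is 0.5 × δ. The documents give no δ. Assuming δ = 0.25 to 0.5 for illustration only, the shift is 0.125 to 0.25 SD. The chance standard error with 50 per arm is √(2/50) = 0.20 SD, so the low end is below ordinary chance imbalance.

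**3. Setting.** Section 23.1 gives 3R's 20 hours a week at 4 hours a day, Monday to Friday, with durations generally of 90-120 days. It gives 2118 the same daily hours, days and duration. NUWAY III is residential, with capacity 31. The contrast is residential against outpatient.

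Enrolment per site is not stated, so site sizes are assumptions. Under simple unstratified allocation, the binomial(n, 0.5) chance of a 70:30 or worse split within a site is:

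| Assumed n at site | Chance |
|---|---|
| 10 | 34% |
| 15 | 12% |
| 20 | 11.5% |
| 30 | 4% |

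These figures do not apply to pairs. If 20 of 100 participants come from one site and fall at random across 50 pairs, summing over the number of complete within-site pairs gives 7.8% for 14:6 or worse. If that site's participants were paired with each other throughout, the chance would be zero. The 50% predictability figure and the 11.5% imbalance figure belong to different designs and cannot be added.

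**The case against.** The strongest reply is that foreseeable assignments are not shown. A pair is never defined. If two people already found eligible were drawn together, neither assignment would be known beforehand. REDCap is offered in the same sentence, so the plan is not committed to pairs, and the documents do not say who generates or holds the sequence. This stands: what is shown is an unresolved choice that permits a predictable method.

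Discretion is also bounded. NUWAY staff pre-screen, counsellors are consulted on doubtful cases, GAIN-SS exclusions are discussed with NUWAY staff, and the cognitive screener and UBACC have numeric cut-offs. That narrows the room for selection but leaves the judgement-based exclusion, the writing-sample assessment and the sobriety waiver.

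The protocol already places randomisation after screening and baseline. The order is right, but it does not help if the next arm can be inferred while screening is under way.

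Finally, the main objective is feasibility and acceptability, and Section 17.3 concedes inadequate power. This limits the consequence. It does not remove it, because the arms will still be compared on outcomes also named as primary.

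**Conclusion.** The point holds as a conditional one. The plan permits an allocation method which, on its natural reading, would make 50% of assignments certain in advance to unblinded staff with eligibility discretion, and it states no concealment. This rests on three assumptions: pairs are blocks of two, they are used sequentially, and staff can see or recall earlier assignments. The resulting bias cannot be sized from the documents. The missing adjustment for setting is a lesser, precision-related gap.

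Four stronger readings are tempting but unsupported:

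- **Staff do know every second assignment.** The text shows only that they could.
- **The arms will differ by 0.125 to 0.25 SD.** The shift behind that range is assumed.
- **The three sites are all very different.** 3R's and 2118 run similar outpatient programmes; only NUWAY III stands apart.
- **Allocation is definitely unstratified, or REDCap is set up to conceal and stratify.** The documents are silent on stratification and name REDCap's procedure without describing its settings.

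This is a worthwhile, inexpensive improvement to a pilot. It is not evidence that allocation has been compromised.

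**What to change.** For remaining enrolment:

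1. Delete the pairs-of-numbers option from Section 5.2 and use only REDCap's randomisation procedure. State the allocation ratio.
2. Have someone not involved in screening prepare a list with varied block sizes. State that the list is concealed from everyone who decides eligibility, and keep block sizes out of the documents those staff use. Varied blocks without concealment would leave about 69% of assignments guessable.
3. Release each assignment only after eligibility and baseline are recorded as final. The protocol already has this order; the addition is an explicit lock.
4. Adjust the arm comparisons for setting (residential versus outpatient). If stratifying, use that single factor at most: waves of 10-20 spread over three site strata would leave many incomplete blocks.
5. Report which method was used for participants already enrolled and, if pairs, how they were drawn.

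The cost is one IRB modification, one list upload in software already used by the study, and one extra covariate. Assignments already made cannot be changed, so item 5 is what lets readers judge them.
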